Follow-Up (Extension Phase) (revised per Amendments 07 and 08)

All subjects, regardless of whether they complete all 48 months of treatment in the Extension Phase or prematurely discontinue study drug, will complete 2 posttreatment Follow-up Visits at 4 and 12 weeks after the last dose of study drug. (revised per Amendment 07) If clinically indicated, more frequent safety assessments can be conducted as part of UNS visits during the Extension Phase Follow-up Period.

Number of Subjects

Approximately 400 MCI/Prodromal or mild to moderate AD subjects will be screened to provide approximately 60 ($\pm 20\%$) randomized subjects (with a target of approximately 15 subjects per treatment arm). There will be no limit to the number of subjects randomized from either clinical cohort. (revised per Amendments 01, 02, 04, and 05)

Inclusion Criteria

Core Study

1. Meets the core clinical research criteria of the NIA-AA for MCI due to AD or AD dementia and is "staged" or classified as either MCI or mild to moderate dementia and also complies with the following: (revised per Amendment 01)

Required at Screening Visit 1:

(revised per Amendment 02)

- a. Subjective Memory Complaint with evidence of concern about a decline in cognition from the subject, caregiver or informant, or clinician's observation
- b. Cognitive impairment of at least 1 SD from age adjusted norms in delayed recall on the ISLT. Alternatively, cognitive impairment of at least 0.5 SD from age-adjusted norms in delayed recall on the ISLT plus impairment of at least 1 SD from age-adjusted norms in at least 1 other computerized learning and memory test (ISLT immediate recall, or 1 of the learning and memory components of the CBB). (revised per Amendment 02)
- c. FAQ ≤ 24 (revised per Amendment 01)

d. MMSE \geq 16 (revised per Amendment 01)

2. Amyloid positive PET image based on centralized PET scan reading; an historical amyloid positive PET scan may be used if conducted within the previous 12 months and provided that the scan and result are considered acceptable by the central PET reading group (revised per Amendment 02)
3. Male or female, age 50 to 85 years, inclusive at time of consent

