8.3 Exploratory Objectives

(revised per Amendments 01, 02, 04, and 05)

The exploratory objectives are:

- To explore the effects of elenbecestat compared on CSF $A\beta(1-40)$ and BACE1 measurements from 4 weeks and up to 18 months of treatment
- To explore the effects of elenbecestat compared with placebo on various biomarkers. Biomarkers to be explored may include, but not limited to:
 - a. CSF biomarkers of neurodegeneration (eg, total tau [t-tau], phosphorylated-tau [p-tau]) after 18 months of treatment
 - b. Plasma and CSF amyloid, and CSF BACE1 measurements from 4 weeks and up to 18 months of treatment (revised per Amendment 06)
 - c. Total hippocampal atrophy at 12 and 18 months of treatment, as measured by volumetric magnetic resonance imaging (vMRI)
 - d. vMRI measurements including left and right hippocampal volume, whole brain volume, and total ventricular volume at 6, 12, and 18 months of treatment
 - e. Brain amyloid levels at 18 months as measured by amyloid positron emission tomography (PET)

-
- To explore the effects of elenbecestat compared with placebo on clinical status at various time points during 18 months of treatment, and during posttreatment follow-up by assessment of:
 - a. The Alzheimer’s Disease Assessment Scale – cognitive subscale (ADAS-cog14)
 - b. The Clinical Dementia Rating (CDR) scale
 - c. The Mini-Mental State Examination (MMSE)
 - d. The International Shopping List Task (ISLT)
 - e. The CogState Brief Battery (CBB)
 - f. The Functional Assessment Questionnaire (FAQ; (also known as the Functional Activities Questionnaire)
 - To explore the relationship between the treatment effects of elenbecestat on measured clinical efficacy scales (eg, MMSE, CDR) and its effects on CSF amyloid, CSF amyloid isoforms, brain amyloid, and vMRI
 - To explore relationships between both elenbecestat dose and exposure, with PD and safety endpoints

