notion that such subjects are on similar trajectories as those with mild AD-dementia. Lower levels of CSF A β 42, amyloid positivity on PET imaging, and higher levels of CSF t-tau in addition to the presence of the *ApoE4* allele have all been associated with greater rates of brain atrophy (Fjell, et al., 2010a; Fjell, et al., 2010b) and will be entered as covariates in various analyses. Hippocampal atrophy has also been shown to predict clinical progression independently of amyloid levels in the brain (Jack, et al., 2010), and this measure will be entered as a covariate in the analysis of the clinical endpoints along with the aforementioned variables.

Brain volume (total ventricular volume, whole brain, temporal lobe) generally shows a modest correlation with performance on a number of cognitive scales (Hua, et al., 2009; Hua, et al., 2010; Freeborough, et al., 1997; Leung, et al., 2010). Using volumetric analysis performed at 6-month intervals during the Core Study and at Month 24 and Month 48 of the Extension Phase, these relationships and the effects of elenbecestat treatment will be explored further. Subjects who discontinue early from the Extension Phase will have safety brain MRI and vMRI assessments at the ED Visit if these assessments have not already been performed during the preceding 90 days. (revised per Amendments 07 and 08) Recent advances in analysis software have made structural imaging more sensitive to detect small changes and able to reliably measure rates of atrophy at these intervals, particularly in the posterior parietal and the lateral temporal regions during the early stages of disease (Hua, et al., 2009; Hua, et al., 2010). Given these observations, a demonstration of significant slowing or stabilization in the rate of atrophy in response to treatment, compared with placebo, will offer further support for disease modification.

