9.7 Statistical Methods

All statistical analyses will be performed by the sponsor or designee. Statistical analyses will be performed using SAS software or other validated statistical software as required.

All statistical tests will be based on the 5% (2-sided) level of significance. (revised per Amendment 05)

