9.7.1.6.3 EXPLORATORY EFFICACY ANALYSES

(revised per Amendments 01, 02, 04, and 05)

An MMRM will be used to analyze the following exploratory endpoints:

- Change from baseline in CSF A β (1-40) and BACE1 variables (eg, activity and protein levels) from 4 weeks and up to 18 months. Data from early discontinuations will also be included. (revised per Amendment 04)
- Change from baseline in CSF biomarkers of neurodegeneration (eg, t-tau and p-tau) at 18 months of treatment
- Change from baseline in plasma amyloid measurements from 4 weeks and up to 18 months of treatment, and during posttreatment follow-up
- Change from baseline in CSF amyloid and CSF BACE1 measurements from 4 weeks and up to 18 months of treatment (revised per Amendment 06)
- Change from baseline in total hippocampal atrophy at 12 and 18 months as measured by vMRI
- Change from baseline in left and right hippocampal, whole brain, and total ventricular volume at 6, 12, and 18 months as measured by vMRI
- Change from baseline in Amyloid PET SUVR composite at 18 months for brain amyloid levels

The following efficacy endpoints will be summarized using descriptive statistics:

- Change from baseline in the clinical assessments: ADAS-cog14, CDR, MMSE, ISLT, CBB, and FAQ at 12 weeks and at 6, 9, 12, 15, 18, 19, and 21 months

The relationship between efficacy endpoints and biomarker endpoints will be explored using correlation analysis.

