9.7.1.7.2 PHARMACODYNAMIC, PHARMACOGENOMIC, AND OTHER BIOMARKER ANALYSES

Pharmacodynamic, PGx, and other biomarker analyses may be performed and reported separately. Details of these analyses may be described in a separate statistical analysis plan. Please also refer to [Appendix 3](#).

Pharmacodynamic Analyses

The PD Analysis Set will be used for the summaries and analyses of PD biomarkers (CSF and plasma biomarkers, MRI endpoints). The percentage change from baseline in CSF A β (1-x), A β (1-42), A β (1-40), t-tau, p-tau, and BACE1 variables (eg, activity and protein levels) from 4 weeks and up to 18 months of treatment will be analyzed and presented graphically. (revised per Amendment 05) Baseline levels and changes in t-tau and p-tau will be correlated with changes in CSF A β (1-42), imaging markers, and *ApoE4* status. (revised per Amendment 04)

Summary statistics for CSF biomarkers will be assessed for evidence of a dose relationship.

Pharmacokinetic and Pharmacodynamic Analyses

The PK/PD relationship between CSF biomarker levels, amyloid load on PET, vMRI, and elenbecestat dose, plasma, and CSF exposure will be initially explored graphically and any emergent relationship will be explored through population PK/PD modeling. The PK/PD relationship between plasma PK parameters with other biomarkers may also be explored using similar methods. (revised per Amendment 04)

The relationship between plasma and CSF exposure to elenbecestat and the clinical efficacy scales (eg, MMSE, CDR) will be explored graphically. Additionally, the relationship between plasma exposures of elenbecestat and select lymphocyte parameters will be explored graphically, and any emergent relationship will be explored using population-based modeling methods. (revised per Amendment 04)

Exposure-safety analyses may also be conducted.

Pharmacogenomic Analyses

Blood samples will be used to determine the *ApoE* genotype and the *NAT2* phenotype of subjects enrolled in this study. The genomic DNA samples may also be stored and used as described in [Section 9.7.1.7.2](#). Details of PGx testing may be provided and reported separately.

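### The objective asks how the drug's effects on clinical scales and on biomarkers relate, but correlating the endpoints cannot by itself answer it

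*Protocol*

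**What the plan says.** Section 8.3 (and the synopsis) lists as an exploratory objective "To explore the relationship between the treatment effects of elenbecestat on measured clinical efficacy scales" and its effects on CSF amyloid and its isoforms, brain amyloid and vMRI. The thing to be related is a pair of drug effects.

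Section 9.7.1.6.3 (and the synopsis) then says: "The relationship between efficacy endpoints and biomarker endpoints will be explored using correlation analysis". No arm, placebo contrast or treatment term is named. For the clinical side, the same section says "The following efficacy endpoints will be summarized using descriptive statistics" and lists "Change from baseline in the clinical assessments: ADAS-cog14, CDR, MMSE, ISLT, CBB, and FAQ". The CSF, plasma, vMRI and PET biomarkers are given an MMRM.

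Section 9.7.1.7.2 adds further correlations, for example "Baseline levels and changes in t-tau and p-tau will be correlated with changes in CSF" amyloid, imaging markers and genotype. It also plans plots of drug exposure against clinical scales. Neither relates the drug's effect on a scale to its effect on a biomarker.

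Section 9.2.4.4 says that brain volume "generally shows a modest correlation with performance on a number of cognitive scales", and that hippocampal atrophy has been found to predict clinical progression.

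**The concern.** A treatment effect is a difference between randomized groups. A correlation of change scores describes how subjects vary together. Subjects whose disease moves faster can lose more brain volume and more cognition, and this produces a correlation whether or not the drug does anything. Section 9.2.4.4 gives reason to expect such a link for vMRI.

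The correlation could therefore be sizeable with no drug effect, or unremarkable with a real one. What is at stake is interpretation. A reader of the study report could take a significant coefficient, placed under an objective worded as treatment effects, to mean that the drug's two effects go together. The protocol names no clinical treatment-minus-placebo estimate to set beside the biomarker MMRM, so nothing in the stated plan corrects that reading.

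**Working it through.** The protocol gives no sample size, power or effect size for this analysis, so there is no figure of its own to reproduce. The check asks how often a test of zero correlation would be significant when the drug affects neither measure.

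**Inputs**
- Arm size: "with a target of approximately 15 subjects per treatment arm" (synopsis), 4 arms, so 4 × 15 = 60; the ±20% allowance gives 48 to 72.
- Level: "All statistical tests will be based on the 5% (2-sided) level of significance" (Section 9.7).
- Natural correlation ρ between change in the scale and change in the biomarker: not given; assumed 0.2 to 0.4, with 0.1 as a low case.
- Pearson test, pooled or within arm: assumed, because Section 9.7.1.6.3 names neither a test nor a unit.

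**Formula (Fisher z)**

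P(significant) ≈ Φ(atanh(ρ)·√(n−3) − 1.96) + Φ(−atanh(ρ)·√(n−3) − 1.96)

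With n = 60, √57 = 7.550:
- ρ = 0.2: 0.2027 × 7.550 = 1.531; Φ(−0.429) = 0.334
- ρ = 0.3: 0.3095 × 7.550 = 2.337; Φ(0.377) = 0.647
- ρ = 0.4: 0.4236 × 7.550 = 3.198; Φ(1.238) = 0.892

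The second term is negligible in each case.

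**Simulation** (40,000 trials per setting, bivariate normal changes, no drug effect on either)

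| ρ | Pooled, n = 60 | Adjusted for arm, n = 60 | One arm of 15 |
|---|---|---|---|
| 0 | 5.0% | 5.1% | 5.2% |
| 0.1 | 12.1% | 11.6% | 6.3% |
| 0.2 | 33.8% | 32.3% | 10.8% |
| 0.3 | 65.3% | 63.0% | 19.3% |
| 0.4 | 89.6% | 88.2% | 32.5% |

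At ρ = 0.3 the pooled figure is 55.4% with 48 subjects and 73.5% with 72. Adjusting for arm changes little. Restricting to one arm lowers the rate mainly because n is smaller.

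**What a real effect adds.** With ρ = 0.3, a true 0.5 SD effect on both measures in all active arms moves the pooled rate only from 65% to 75%. Under these assumptions the coefficient mostly reflects disease course.

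**How to read these rates.** At ρ above zero, zero correlation is false, so rejecting it is right. The percentages are power against a true correlation. They show only that significance here carries little information about the drug.

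**The case against.** The strongest reply is that the protocol fixes less than this point assumes. It does not say subject-level, pooled, Pearson or p-value. Section 9.7.1 says analyses go by treatment group, defined in the SAP, so the pooled illustration is not the stated plan. Section 9.2.4.4 also speaks of covariates in an analysis of the clinical endpoints, so the SAP may hold a clinical model. This limits the figures but does not remove the mismatch: by-group correlation is still association among subjects, and Section 9.2.4.4 names no treatment contrast for the scales. Correlating the four arm means would show little excess (6.3% at ρ = 0.3), but it rests on four points, and the Amendment 06 re-assignment erodes the dose contrasts later in treatment.

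Four stronger readings are tempting, and the documents do not support them:
- *Inflated type I error.* A reader might set 34% to 90% against the nominal 5%. The null being tested is zero correlation, and it is false in those settings.
- *A route to a wrong surrogate claim in Phase 3.* Section 9.2.4.4 rests disease modification on slower atrophy than placebo, not on this correlation. Section 7.1 shows the Phase 3 dose was chosen on safety and CSF amyloid reduction. No decision rule uses the correlation.
- *The same mismatch in the Extension.* Appendix 6 repeats the correlation sentence, but its objectives ask for no relationship between treatment effects.
- *A quantified problem for CSF amyloid.* The size of the voluntary CSF subset is not stated, and no natural link between CSF change and clinical change is documented.

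It is also fair to say that correlation is an ordinary tool for describing how biomarkers and scales move together, which Section 9.2.4.4 also wants to explore.

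**Conclusion.** The mismatch between objective and method stands and is minor. Section 8.3 asks about linked treatment effects; Section 9.7.1.6.3 correlates endpoints and leaves the clinical scales to descriptive summaries. Subject-level correlation, pooled or by arm, cannot by itself answer that objective.

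The size, about 34% to 90% of trials significant with no drug effect, is an illustration. It rests on assumed correlations of 0.2 to 0.4, a pooled Pearson test and 60 complete pairs. The case is clearest for vMRI, where the protocol itself describes the disease link, and weaker for CSF amyloid. Because the analysis is exploratory and nothing depends on it, the consequence is one of interpretation, and the point is a cheap improvement.

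**What to change.** In Section 9.7.1.6.3 and the synopsis:

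1. Address the objective with the treatment-minus-placebo difference and 95% CI on the clinical scale and on the biomarker at the same visit, side by side. Shared visits exist: 6, 12 and 18 months for vMRI (12 and 18 for total hippocampal volume), and 18 months for amyloid PET and CSF.
2. Define the treatment groups for this display so that they respect the Amendment 06 dose re-assignment.
3. Show any correlation by treatment group, with the placebo group as the natural-history reference, and label it association rather than a relationship of treatment effects.

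A regression of clinical change on biomarker change with a treatment interaction should not be offered as the answer: its slopes are still subject-level associations, and a uniform drug effect leaves them unchanged.

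The cost is wording and a little programming on data already collected. The drawback is precision. For two arms of 15, the 95% half-width is about 1.96 × √(2/15) = 0.72 SD, and it is wider in the voluntary CSF subset. The display will therefore be descriptive.

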9.7.1.7 Pharmacokinetic, Pharmacodynamic, Pharmacogenomic, and Other Biomarker Analyses

9.7.1.7.1 PHARMACOKINETIC ANALYSES

The PK Analysis Set will be used for elenbecestat concentration listings and for summaries of elenbecestat concentrations in plasma and CSF by dose and day. Elenbecestat metabolite PK data may also be listed and summarized. (revised per Amendment 04)

A population PK approach will be used to characterize the plasma PK of elenbecestat. For this approach, plasma PK data from this study will be pooled with relevant data from Phase 1 studies. As appropriate, the effect of covariates on the PK of elenbecestat will be evaluated. The PK model will be parameterized for oral clearance (CL/F) and apparent volume of distribution (V_z/F) for elenbecestat. Derived exposure parameters such as steady state AUC and average concentration (C_{avg}) of elenbecestat and other derived parameters will be calculated from the model using the individual estimates parameterized for oral clearance and dosing history. (revised per Amendment 04)

9.7.1.7.2 PHARMACODYNAMIC, PHARMACOGENOMIC, AND OTHER BIOMARKER ANALYSES

Pharmacodynamic, PGx, and other biomarker analyses may be performed and reported separately. Details of these analyses may be described in a separate statistical analysis plan. Please also refer to [Appendix 3](#).

Pharmacodynamic Analyses

The PD Analysis Set will be used for the summaries and analyses of PD biomarkers (CSF and plasma biomarkers, MRI endpoints). The percentage change from baseline in CSF A β (1-x), A β (1-42), A β (1-40), t-tau, p-tau, and BACE1 variables (eg, activity and protein levels) from 4 weeks and up to 18 months of treatment will be analyzed and presented graphically. (revised per Amendment 05) Baseline levels and changes in t-tau and p-tau will be correlated with changes in CSF A β (1-42), imaging markers, and *ApoE4* status. (revised per Amendment 04)

Summary statistics for CSF biomarkers will be assessed for evidence of a dose relationship.

Pharmacokinetic and Pharmacodynamic Analyses

The PK/PD relationship between CSF biomarker levels, amyloid load on PET, vMRI, and elenbecestat dose, plasma, and CSF exposure will be initially explored graphically and any emergent relationship will be explored through population PK/PD modeling. The PK/PD relationship between plasma PK parameters with other biomarkers may also be explored using similar methods. (revised per Amendment 04)

The relationship between plasma and CSF exposure to elenbecestat and the clinical efficacy scales (eg, MMSE, CDR) will be explored graphically. Additionally, the relationship between plasma exposures of elenbecestat and select lymphocyte parameters will be explored graphically, and any emergent relationship will be explored using population-based modeling methods. (revised per Amendment 04)

Exposure-safety analyses may also be conducted.

Pharmacogenomic Analyses

Blood samples will be used to determine the *ApoE* genotype and the *NAT2* phenotype of subjects enrolled in this study. The genomic DNA samples may also be stored and used as described in [Section 9.7.1.7.2](#). Details of PGx testing may be provided and reported separately.

9.7.1.8 Safety Analyses

Evaluations of safety will be performed on the Safety Analysis Set. The incidence of AEs (including changes from baseline in physical and neurological examinations, and dermatological assessments), out-of-normal-range laboratory safety test variables, abnormal ECG findings, out-of-range vital signs, suicidality (C-SSRS), and results of the sleep questionnaire, along with the change from baseline in laboratory safety test variables, ECGs, safety MRI, vital sign measurements, and cognitive decline assessment such as CBB will be summarized by treatment group using descriptive statistics. (revised per Amendment 05)

9.7.1.8.1 EXTENT OF EXPOSURE

The extent of exposure to study drug will be summarized as cumulative extent of exposure in 3-month intervals. The cumulative number and percent of subjects will be presented by treatment group. Duration of exposure will be summarized using descriptive statistics as continuous variable as well as categorical variable in 3-month intervals and the number and percent of subjects will be presented by treatment group.

9.7.1.8.2 ADVERSE EVENTS

The AE verbatim descriptions (investigator terms from the eCRF) will be classified into standardized medical terminology using the Medical Dictionary for Regulatory Activities (MedDRA). Adverse events will be coded to the MedDRA (Version 17.0 or higher) lower level term closest to the verbatim term. The linked MedDRA preferred term and primary system organ class (SOC) are also captured in the database.

A TEAE is defined as an AE that emerges during treatment, having been absent at pretreatment (Baseline) or

- Reemerges during treatment, having been present at pretreatment (Baseline) but stopped before treatment, or
- Worsens in severity during treatment relative to the pretreatment state, when the AE is continuous.

Only those AEs that are treatment-emergent will be included in summary tables. All AEs, treatment-emergent or otherwise, will be presented in subject data listings.

The TEAEs will be summarized by treatment group on the Safety Analysis Set. The incidence of TEAEs will be reported as the number (percentage) of subjects with TEAEs by SOC and preferred term. A subject will be counted only once within an SOC and preferred term, even if the subject experienced more than 1 TEAE within a specific SOC and preferred term. The number (percentage) of subjects with TEAEs will also be summarized by maximum severity (mild, moderate, or severe). The number (percentage) of subjects with TEAEs will also be summarized by relationship to study drug (Yes [related] and No [not related]).

The number (percentage) of subjects with treatment-related TEAEs will be summarized by SOC and preferred term. Treatment-related TEAEs include those events considered by the investigator to be related to study drug. The number (percentage) of subjects with treatment-related TEAEs will also be summarized by maximum severity (mild, moderate, or severe).

Adverse events will be summarized by the following subgroups: *ApoE4* status (positive or negative), prior treatment with AChEIs or memantine (no or yes), and clinical population (MCI/Prodromal or mild to moderate AD). (revised per Amendment 01)

The number (percentage) of subjects with TEAEs leading to death will be summarized by MedDRA SOC and preferred term for each treatment group. A subject data listing of all AEs leading to death will be provided.

The number (percentage) of subjects with treatment-emergent SAEs will be summarized by MedDRA SOC and preferred term for each treatment group. A subject data listing of all SAEs will be provided.

The number (percentage) of subjects with TEAEs leading to discontinuation from study drug will be summarized by MedDRA SOC and preferred term for each treatment group. A subject data listing of all AEs leading to discontinuation from study drug will be provided.

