In the MAD study, AEs of interest included relapse of orolabial herpes, viral respiratory tract infection, drug rash, and abnormal dreams. More details are available in the Investigator's Brochure. In summary, elenbecestat administered at doses of 200 and 400 mg was associated with reductions in CD4 (T helper cells), CD8 (cytotoxic T cells), and CD19 (B cells) counts at Day 8. These reductions were more clearly evident by Day 15, consistent with a treatment by time interaction in the statistical analysis. There was evidence that the lower doses of 50 to 100 mg also caused some reduction in CD4 lymphocyte counts by Day 15. Doses above 100 mg appeared to be associated with greater reductions in CD4 and CD8 lymphocyte counts, which occurred earlier in the treatment period compared with the effects of 25 to 100 mg doses. These effects on lymphocyte counts gradually resolved from Day 20 to Day 35, which were 6 and 21 days, respectively, after administration of the last dose of elenbecestat on Day 14. Reductions in CD4 and CD8 lymphocyte counts at doses of 200 and 400 mg to a level close to or less than the lower limit of normal (LLN) could be associated with increased risk of developing relapse of orolabial herpes or other infections.

In Study 003, a drug-drug interaction study, PK results showed that itraconazole (a potent inhibitor of cytochrome P450 [CYP]3A4 and carboxylesterase-2 [CES2]) increased by approximately 70% the AUC of elenbecestat. Consequently, strong inhibitors of CYP3A4 will be prohibited in this study.

Rifampin (a potent CYP3A4 inducer) caused a mild decrease (by approximately 20%) of the AUC of elenbecestat. Therefore, no restrictions are required for the use of concomitant medications which are known to be inducers of CYP450 enzymes. Donepezil (a moderate CES2 inhibitor) caused a mild increase (by approximately 20%) of the AUC of elenbecestat when coadministered with elenbecestat but not when dosed at least 2 hours apart from elenbecestat. Elenbecestat (which inhibits the P-glycoprotein 1 transporter) did not affect the PK properties of digoxin. Nonclinical studies also indicated that other CYP pathways apart from CYP3A4 would not be major pathways of metabolism of elenbecestat. Therefore, on the basis of drug interaction considerations, the only restriction of concomitant medications is that for strong inhibitors of CYP3A4.

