9.5.1.5.1 ADVERSE EVENTS AND EVENTS ASSOCIATED WITH SPECIAL SITUATIONS

An AE is any untoward medical occurrence in a subject or clinical investigation subject administered an investigational product. An AE does not necessarily have a causal relationship with the medicinal product. For this study, the study drug is elenbecestat.

The criteria for identifying AEs in this study are:

- Any unfavorable and unintended sign (including an abnormal laboratory finding), symptom, or disease temporally associated with the use of an investigational product, whether or not considered related to the investigational product (Note: It is not necessary to report every sign or symptom as a separate AE if the overall disease [diagnosis] is being reported as an AE.)
- Any new disease or exacerbation of an existing disease
- Any deterioration in nonprotocol-required measurements of a laboratory value or other clinical test (eg, ECG or x-ray) that results in symptoms, a change in treatment, or discontinuation of study drug
- Recurrence of an intermittent medical condition (eg, headache) not present pretreatment (Baseline)
- An abnormal laboratory test result should be considered an AE if the identified laboratory abnormality leads to any type of intervention, discontinuation of study drug, or withholding of study drug, whether prescribed in the protocol or not

All AEs observed during the study will be reported on the eCRF. All AEs, regardless of relationship to study drug or procedure, should be collected beginning from the time the subject signs the study ICF through the last visit during the Core Study (Visit 20, as shown in [Table 7](#), for subjects who do not enter the Extension Phase) or the last Visit during the Extension Phase (Follow-up Week 12 Visit as shown in [Table 14](#), for subjects who participate in the Extension Phase). (revised per Amendment 07) Subjects who fail screening primarily due to AE(s) must have the AE(s) leading to screen failure reported on the Screening Disposition eCRF. SAEs will be collected for 3 months after the last dose of study drug, (ie, through to the final Follow-up visit [Visit 20 for subjects who do not enter the Extension Phase or Follow-up Week 12 Visit for subjects who participate in the Extension Phase]). (revised per Amendments 04, 05, and 07)

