9.7.1.1 Study Endpoints

9.7.1.1.1 PRIMARY ENDPOINT

- Safety and tolerability, which include incidence of TEAEs and SAEs, laboratory parameters, vital signs, and ECG parameters (revised per Amendment 05)

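### AEs, SAEs and fatal events that begin in the 12-week Follow-up Period are listed but enter no AE, SAE or death incidence table, so the SAE table is narrower than the primary endpoint

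*Protocol*

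**What the plan says.** **Definition.** Section 9.7.1.8.2 begins: "A TEAE is defined as an AE that emerges during treatment, having been absent at pretreatment (Baseline) or". The other two limbs cover an event that comes back after stopping before treatment and a continuing event that becomes more severe. Both also have to happen during treatment. No calendar end to that period is given.

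**Tabulation rule.** The same section says "Only those AEs that are treatment-emergent will be included in summary tables" and sends the rest to listings: "All AEs, treatment-emergent or otherwise, will be presented in subject data listings".

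**Deaths and SAEs.** The death table carries the same restriction: "The number (percentage) of subjects with TEAEs leading to death will be summarized by MedDRA SOC and preferred term for each treatment group". So does the SAE table: "The number (percentage) of subjects with treatment-emergent SAEs will be summarized by MedDRA SOC and preferred term for each treatment group".

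**Primary endpoint.** Section 9.7.1.1.1 reads: "Safety and tolerability, which include incidence of TEAEs and SAEs, laboratory parameters, vital signs, and ECG parameters". SAEs stand there without a treatment-emergent qualifier.

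**Collection.** Section 9.5.1.5.1 collects all AEs from consent to the last Core Study visit (Visit 20) and adds "SAEs will be collected for 3 months after the last dose of study drug". Section 9.5.4.1 repeats the 3-month SAE window.

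**Periods.** Sections 9.1 and 9.1.2 split the Randomization Phase into a Treatment Period of 78 weeks and a Follow-up Period of 12 weeks after the last dose. Section 9.1.2.3 requires follow-up visits at 2, 4, 8 and 12 weeks from everyone, including those who stop drug early.

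**The concern.** The trial collects AEs for three months after the last dose, and its only primary endpoint is safety. The tabulation rule then leaves that period out of every table that gives an AE, SAE or death incidence by arm. A listing shows that an event happened but gives no incidence by treatment group, and incidence is what the endpoint asks for.

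The protocol itself treats follow-up as relevant to safety. The primary objective (Section 8.1) covers immunological and hematological parameters. Blood counts and lymphocyte subsets are drawn at all four follow-up visits. Section 9.3.3 keeps subjects who are stopped with an infection under observation for at least 12 weeks. On the earlier multiple-dose study, Section 7.2 says: "These effects on lymphocyte counts gradually resolved from Day 20 to Day 35, which were 6 and 21 days" after the last dose. A new infection or SAE two weeks after stopping is within what the follow-up is designed to detect, yet it would be counted in no AE or SAE table.

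**Working it through.** **1. Length of follow-up.** Table 7 puts Visit 18 (end of treatment) at Day 547 and 78 weeks elapsed, and Visit 20 at Day 631 and 90 weeks elapsed.
- By days: (631 − 547) / 7 = 12.0 weeks.
- By weeks elapsed: 90 − 78 = 12 weeks.

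Both agree with the stated 12-week Follow-up Period. (The Week 8 follow-up column shows Day 589, which is (589 − 547) / 7 = 6 weeks after Day 547, against 86 − 78 = 8 weeks in the weeks-elapsed row. This needs reconciling but does not affect the present point.)

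**2. Does the treatment-emergent window reach into follow-up?**
- Sections 9.1 and 9.1.2 define treatment and follow-up as separate periods.
- Section 9.7.1.5 ends concomitant medication at the last dose and handles the 12-week follow-up separately.
- Section 9.7.1.8.3 takes end of treatment as the last on-treatment value.
- No section adds a post-dose window for TEAEs.

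On the text, the answer is no.

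**3. Endpoint against tables, for an event with onset after the last dose.**
- AE: collected to Visit 20; listed; in no summary table.
- SAE: collected for 3 months and named without limit in the primary endpoint; listed; not in the SAE table.
- Fatal event: listed; not in the death table. A fatal event that began on treatment is still counted, even if death comes later.

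**4. Share of post-first-dose AE collection time that feeds no AE table.** Share = 12 / (T + 12), where T is weeks on drug.
- T = 78 (completer): 12/90 = 13.3%
- T = 26: 12/38 = 31.6%
- T = 12: 12/24 = 50%
- T = 4: 12/16 = 75%

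The three early-stop values are examples; the protocol gives no discontinuation rate.

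**5. What one uncounted subject is worth.** With the planned 15 per group (Section 9.7.2), one subject is 1/15 = 6.7 percentage points of an arm's incidence.

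**6. Illustration under assumed risks.** The protocol gives no follow-up event rate. Let p be the chance that a subject has an event in follow-up that would otherwise have been counted, independent between subjects. Then P(at least one uncounted subject in an arm of 15) = 1 − (1 − p)^15, and the expected number among 60 is 60p.
- p = 1%: 14%; 0.6 subjects
- p = 5%: 54%; 3 subjects
- p = 10%: 79%; 6 subjects
- p = 20%: 97%; 12 subjects

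**7. Extension Phase.** Appendix 6 analyzes safety in the same way as the Core Study, so the rule carries over. For a completer, 208 weeks of treatment and 12 of follow-up give 12/220 = 5.5%.

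**The case against.** The strongest reply is that the definition gives no dates. Elsewhere the protocol names the last dose or the Treatment Period explicitly, and the TEAE definition does neither, so a dated window could sit in the SAP. Only the protocol was available for this review. However, Section 9.7.1 defers treatment-group definitions and the dose re-assignment analyses to the SAP; it does not defer the TEAE definition or the rule on what is tabulated, and Section 9.7.1.8.2 states both. If the phrase is thought open, two programmers could build different tables from it, which is a further reason to date it.

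Other objections limit the reach of the point, and they stand:
- A reader might infer that every primary-endpoint table is affected. Laboratory results (lymphocyte subsets and immunoglobulins included), vital signs and ECGs are summarized by postbaseline visit (Sections 9.7.1.8.3 to 9.7.1.8.5), so follow-up values can appear there.
- Nothing is lost from the record. All AEs, all SAEs and all AEs leading to death are listed, and with about 15 subjects per arm the listings can be read in full.
- A subject counts once per system organ class and preferred term. Someone stopped for an infection is already counted in that class, so a second infection adds at most a preferred-term row.
- A reader might infer from Section 7.2 that drug-related events are to be expected in follow-up. The lymphocyte reductions were clearest at 200 and 400 mg, and Section 9.4.4 reports no infection or drug rash at 100 mg or below in that study; the top dose here is 50 mg.

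**Conclusion.** The point holds for the AE, SAE and death incidence tables. As written, events with onset in the 12 weeks after the last dose are listed but enter none of them, and the SAE table covers less than the primary endpoint and less than the SAE collection window.

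The size is 13% of post-first-dose AE collection time for a completer and more for anyone who stops early. This is a share of calendar time, not of events. The at-least-one-subject figures rest on assumed risks and independence between subjects and show scale only.

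A reader might go further and conclude that the rule removes events mainly from the active arms and so biases the result toward no harm. The documents give no follow-up event rates by arm, so neither the direction nor the amount of any distortion can be stated. The conclusion also assumes that treatment ends at the last dose, as the protocol's own division of periods indicates, and that no SAP text overrides it.

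**What to change.** Before database lock:
1. Tabulate by treatment group all SAEs and all AEs leading to death from first dose through the final Follow-up Visit, or to the day before the first Extension dose if that is earlier. This brings the SAE table into line with Section 9.7.1.1.1.
2. For AEs in general, either give the TEAE definition that same dated end, or keep the on-treatment definition and add a separate column for onset after the last dose. The second option keeps the on-treatment incidence visible.
3. Apply the same rule to the Extension tables, through the Follow-up Week 12 Visit.

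Cost: one definition and one extra column, with no new data. A small downside is that some unrelated late events will be counted in all arms.
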